This search will use ICD-10 codes as defined by the UK biobank Outcome Adjudication Group (Definitions of Stroke for UK Biobank Phase 1 Outcomes Adjudication Date: August 2017 Version: 1.1 https://biobank.ndph.ox.ac.uk/showcase/showcase/docs/alg_outcome_stroke.pdf). This will identify the following events:

- 1. Admission to hospital with aneurysmal subarachnoid haemorrhage (I60.0-I60.7)
- 2. Occlusive treatment of aneurysm.
- 3. Death diagnosed as subarachnoid haemorrhage in parts 1a-c of the death certificate.

All patients identified from the HES search with any of the above events will then have their medical notes re-evaluated by the local neurosurgery unit to confirm the HES report has accurately identified the event as aneurysm rupture or treatment.

A similar search will be repeated in Wales using NWIS/PEDW where NHS numbers are also used. Scotland does not use NHS numbers making searches more complex. However, a further search of equivalent database (SMR01) will be performed in Scotland using name and date of birth for identification.

Data collection - quality assurance - central HES ONS data

Additionally, all patients will be checked for possible SAH events that could have been miscoded.

Therefore, any patients with the codes:

- 1. Subarachnoid haemorrhage (other and unspecified) (I60.8-60.9)
- 2. Intracerebral haemorrhage (including intraventricular haemorrhage (I61.0-61.9)
- 3. Non-traumatic subdural haemorrhage (I62.00-I62.02)
- 4. Traumatic subarachnoid haemorrhage (S06.6X0, S06.6X9A, S06.6X9, S06.6X8A)

will have their casenotes reviewed for evidence the haemorrhage was aneurysmal.

Any patients with the following codes:

- 5. I46.1 sudden cardiac death
- 6. R96 other sudden death cause unknown
- 7. R98 unattended death

will have their casenotes reviewed to assess if their death was likely due rupture of their aneurysm.

Additionally, in at least one pilot site, all patients with the code

8. Cerebral infarction (63.0-63.9 & I64.X)

will have their casenotes reviewed to estimate rates of missed diagnosis for the whole cohort.

Where verification cannot be established from medical notes, any patients with codes in the specified possible miscoded SAH events will be assumed to be non-aneurysmal unless they have a procedure code indicating occlusive treatment of aneurysm within 30 days after the event, or they were coded as

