subarachnoid haemorrhage other or unspecified and they subsequently died within 30 days (based on the very low rate of mortality from non-aneurysmal SAH) and did not have any additional codes for trauma indicating a non-aneurysmal event.

Data collection - other considerations - central HES ONS data

Last follow-up for each patient will be set as the time at which the HES search was performed, or the patient was unregistered with a GP in the UK or date of death, or the aneurysm was treated, whichever is earliest.

Additionally, we will record

- 1. race
- 2. I10 essential (primary) hypertension
- 3. Z72.0 tobacco use
- 4. F17.2 tobacco dependence

And use these to complete any missing baseline data. Where baseline data and HES conflict, the baseline data will be used. Where neither is available, after assessment for any bias (missing completely at random MCAR, missing at random MAR, missing not at random MNAR) multiple imputation will be used.

Statistical analysis - Aim 1 - PHASES validation

The PHASES study provides the coefficients from their Cox regression model and baseline survival at 5 years that allows the absolute 5-year risk of rupture, to be calculated for all patients who are not censored before 5 years, using age, whether the patients has hypertension, history of SAH, size of aneurysm (3 categories) and location of aneurysm. The time to censoring will be calculated (death or date of HES search or date unregistered from GP practice whichever is first) to ensure 5 years of follow up if rupture has not occurred. Discrimination will be assessed using Harrell's C-index of concordance and Royston and Sauerbrei's D statistic. Calibration will be assessed at the 5 year time point using the method in Royston (2014). These will be used to calculate the number of SAH events per 5 years for each PHASES score (0 to 12+) and expressed as a percentage with 95% confidence interval to compare to the PHASES estimates.

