There are multiple potential causes leading to underestimates of rupture risk. The magnitude of these will be estimated and corrected for. In view that all SAH events will be verified in clinical notes it is not expected that there will be any significant overestimation and consequently correction. Events may be missed due to migration. Any patients noted at time of baseline data collection to have emigrated will have this recorded and this will be used for censoring. Additionally, HES data will reveal any patients who have unregistered with their GP for emigration which will be used as a censoring event. Unfortunately, it is anticipated that not all patients will unregister on departure from the UK and therefore the observed emigration rate (that from the baseline data collection and HES data) will be subtracted from average national migration figures and this applied to the data.

Events may be missed due to miscoding. Aneurysmal SAH miscoded as:

1. Cerebral infarction (63.0-63.9 & I64.X)

Will be identified at one or more test sites by review of clinical notes to estimate any under-estimates due to miscoding and these estimates applied to the whole cohort.

In the event there are high rates of failed verification for the codes:

- 1. Intracerebral haemorrhage (including intraventricular haemorrhage (I61.0-61.9)
- 2. Subarachnoid haemorrhage (other and unspecified) (I60.8-60.9)
- 3. Non-traumatic subdural haemorrhage (I62.00-I62.02)
- 4. Traumatic subarachnoid haemorrhage (S06.6X0, S06.6X9A, S06.6X9, S06.6X8A)
- 5. I46.1 sudden cardiac death R98 unattended death
- 6. R96 other sudden death cause unknown
- 7. R98 unattended death

at some centres, then error estimates may be applied to the data from centres with robust code verification.

Additionally, at baseline data collection, any subsequent SAH events observed in the local notes will be recorded with their date, or date of last follow up. The SAH events observed during this follow up period will be compared to that for the similar period using HES data (after applying the above corrections), and the total risk estimates adjusted for any differences between these to give final 5 year risk estimates.

Discrimination will be assessed with the C statistic but is expected to be poor due to low event rates and therefore will be compared to the original PHASES data. Calibration will be assessed with calibration plots and Hosmer-Lemeshow tests.

Statistical analysis – Aim 2 - Additional prognostic factors

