A new risk prediction model for rupture will be developed using the total data set, including the additional possible risk factors. The Cox regression model will be used for risk of rupture. The absolute risks can be estimated at relevant time intervals, 2, 5 and 10 years. Numbers of missing values will be summarised for each factor. Multiple imputation will be used to replace missing values. Discrimination of the final model will be assessed with the Harrell's c-statistic. Internal validity will be assessed by bootstrap resampling.

Additionally, the following sensitivity analyses will be performed:

In view that a significant number of aneurysms are anticipated to have grown and subsequently treated on follow up, any cases noted to have undergone treatment for aneurysm growth will be included in a model predicting the risk of rupture or treatment for aneurysm growth. In view that it is anticipated that a number of unexplained deaths will be captured where it will not be possible to resolve if the cause was SAH or not, a model predicting aneurysm rupture or unexplained or unattended death (R 96 and 98) will be built.

Statistical analysis - Aim 3 - Long term rupture rates

It is anticipated that initially follow up times will range from months to 15 years. This will be insufficient to definitively answer what the long term risks posed by aneurysms are. However, a model will be built including a term for new diagnosis vs known diagnosis. This will establish if rupture rates are similar between patients with new and prior diagnoses.

All patients, including those who underwent aneurysm occlusion, will be included in time-to-event analysis which will cover the whole duration of available follow-up. This will include Kaplan-Meier and proportional hazards models for univariate and multivariate survival curve fitting. A cumulative Hazard plot will be used to assess if rupture risk is constant or varies with time from diagnosis.

Longer term, HES searches will be repeated periodically using unique HES identifiers generated by DARS at the first HES search. These searches will identify any late events of SAH due to aneurysm rupture and models will be built to predict true long-term risk.

Data management

Patient confidentiality

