6 STUDY SETTING

The study will be conducted at up to 30 neurosurgery units in the UK. Patient identification and baseline clinical data will be collected from their locally held medical notes and stored on their own NHS servers. Access to patient medical records by the local direct clinical care team will be either electronic or manual depending the document storage method of the individual unit. The identification and baseline data collection by the direct clinical care team, in each neurosurgery unit maximises patient confidentiality and minimises the number of people who have access to identifiable medical records.

The coordinating unit (University Hospitals Southampton NHS FT) will be the site at which patient information is uploaded to HES/PEDW/SMR. It will also be the site where pseudonymised data is analysed. There are no site specific requirements dictating these be done in Southampton however this site has been chosen for analysis as it is the base where [name] and [name] currently work as clinicians. Pseudonymised data may also be analysed by [name] at the University of Oxford although she will have access to the pseudonymised list only. Similarly, pseudonymised data may also be analysed by contributors at participating centres.

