7.3 Recruitment

7.3.1 Sample identification

Patient identification

Due to most UIAs being detected during investigation for other conditions, HES coding for outpatient appointments cannot reliably identify patients with intracranial aneurysms and a local review suggested this may lead to a large underestimate of cases.

Therefore, patients will be identified by the direct clinical care teams at adult tertiary neurosurgical units in the UK treating patients with UIAs. All patients will be eligible whether seen in the centre, scanned in the centre or only discussed with the centre at MDT or on-call. Therefore, more than one search method may be applicable. Search methodology may be adapted to suit local case note and radiology records. We would recommend sequentially performing the following searches:

- 1. Electronic keyword searches of clinic letters, discharge summaries and MDTs. These capture most patients but risk missing patients not formally discussed with neurosurgery.
- 2. Electronic searches of cranial CTA, MRA and DSA reports for the term "aneurysm" excluding "no aneurysm". These searches capture all patients at the parent hospital but may miss regional patients scanned in district hospitals.
- 3. Searches of on call referrals may capture any further conservatively managed UIAs.

In some units, paper records of MDT or vascular clinics may be searched where electronic systems are not in place. Additionally, some units maintain prospective neurovascular databases which could be used for patient identification.

To reduce selection bias all participating centres will produce a written search strategy for their unit and perform a search over a locally prespecified time period. This period will be within the range of 1 January 2006 – 31 December 2020 (representing the implementation of PACS and the present), but may be shorter. The date of inclusion will be the date of the first document to identify the patient in that locally prespecified date range. Where aneurysms were diagnosed before the study dates, the aneurysm will be marked as "known diagnosis" and the date of inclusion remains that of the first document in the study date range.

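### No named Aim 1 or Aim 2 analysis accounts for the recruiting unit, so intervals for overall UK risk and PHASES calibration will be too narrow if units differ

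*Protocol*

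**What the plan says.** Section 6 sets the scale: "The study will be conducted at up to 30 neurosurgery units in the UK". Section 7.3.1 leaves case finding to each unit: "Search methodology may be adapted to suit local case note and radiology records", and "all participating centres will produce a written search strategy for their unit and perform a search over a locally prespecified time period". The local period may be shorter than 2006 to 2020.

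Outcomes are searched centrally in HES/ONS and the Welsh and Scottish equivalents. Patients with a flagged event "will then have their medical notes re-evaluated by the local neurosurgery unit to confirm the HES report has accurately identified the event". Under Aim 1, should many codes go unverified "at some centres, then error estimates may be applied to the data from centres with robust code verification". That is the only device in the analysis text that works at centre level, and it is an optional correction to the estimate, with no variance attached.

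For Aim 1, section 5 names the C-index, the D statistic, Royston's calibration method, calibration plots, Hosmer-Lemeshow tests, and SAH risk by PHASES score "expressed as a percentage with 95% confidence interval to compare to the PHASES estimates". For Aim 2 it names a Cox model, multiple imputation, Harrell's c and a bootstrap: "Internal validity will be assessed by bootstrap resampling". No stratum, frailty, robust variance or cluster resampling by unit is mentioned. The bootstrap's resampling unit is not stated.

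The protocol also standardises the units in part, through a data definitions manual, compulsory training with test cases, and a common rule for events that cannot be verified.

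**The concern.** Observed rupture rates can differ between units for reasons that PHASES does not contain. Search sources and calendar periods differ. A possible miscoded SAH that cannot be verified counts as non-aneurysmal, with limited exceptions, so a unit with poor notes yields fewer events by rule. Missed SAH coded as infarction may be estimated at a single site and applied to everyone. Aneurysm irregularity counts as absent when the radiology report is silent, so one Aim 2 predictor follows local reporting habit.

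The protocol's Background faults PHASES for putting risk differences down to population when study methods also differed. Pooling locally designed searches with no unit term is open to a similar criticism.

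Aim 1 asks whether UK risk agrees with the PHASES prediction. If units vary and the variance ignores it, ordinary between-unit variation can be reported as miscalibration, or UK risk can be quoted with false precision. For Aim 2, a bootstrap of individual patients, if that is what is used, leaves the same units in every resample and cannot show how the model performs in another unit.

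**Working it through.** **The plan's own sizing (section 7.2.1).** The rate is 51/(1,692 × 4.1) = 0.735 per 100 patient-years. Sixty events need 60/(51/1,692) = 1,990.6 patients and 8,161 years, as stated. For polycystic kidney disease, 10/0.00735 = 1,360 years. Dividing by 53/4,436 gives 113,829 years (stated 113,905), and dividing by 5 gives 22,766 patients (stated 22,781). The figures reproduce closely. They come from an events-per-covariate rule and contain no design effect.

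**Inputs for the check.** Five-year risk p = 1 − exp(−5 × 0.00735) = 3.61%. N = 22,781 and K = 30 units, so m = 22,781/30 = 759 per unit. ICC is not given; a range from 0 to 0.01 is assumed.

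**Formulas.** Design effect DE = 1 + (m − 1) × ICC. Actual coverage of a nominal 95% interval = 2Φ(1.96/√DE) − 1. Between-unit SD = √(ICC × p(1 − p)).

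**Pooled five-year risk, inference beyond the participating units:**

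| ICC (assumed) | Between-unit SD, points | DE | SE multiplier | Coverage |
|---|---|---|---|---|
| 0 | 0 | 1.00 | 1.00 | 95% |
| 0.0005 | 0.42 | 1.38 | 1.17 | 90.5% |
| 0.001 | 0.59 | 1.76 | 1.33 | 86% |
| 0.002 | 0.83 | 2.52 | 1.59 | 78% |
| 0.005 | 1.32 | 4.79 | 2.19 | 63% |
| 0.01 | 1.87 | 8.58 | 2.93 | 50% |

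At ICC 0.001 the half-width should be 0.32 points, where the independent-patient formula gives 0.24. A beta-binomial simulation (30 units of 759, 20,000 runs) gave coverage of 95%, 86%, 78% and 62% at ICC 0, 0.001, 0.002 and 0.005. An interval built from the unit means, with t on 29 degrees of freedom, covered 94 to 95% throughout.

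**Smaller cohorts, ICC 0.001, 30 units.** 11,391 patients: m = 380, DE 1.38, coverage 90.5%. The Aim 1 minimum of 1,990: m = 66, DE 1.07, coverage 94%.

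**Per-score intervals.** Assuming 13 equal score groups, m = 22,781/(13 × 30) = 58. DE is 1.06 at ICC 0.001 (coverage 94%) and 1.29 at 0.005 (92%).

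**If the target is exactly the 30 UK units.** DE becomes 1 + (m − 1) × ICC × (1 − K/30). With N held at 22,781 and ICC 0.001:
- K = 30: DE 1.00, coverage 95%.
- K = 25, m = 911: DE 1 + 910 × 0.001 × 1/6 = 1.15, coverage 93%.
- K = 20, m = 1,139: DE 1 + 1,138 × 0.001 × 1/3 = 1.38, coverage 90.5%.

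**Test of a correct PHASES prediction.** In simulation, 20 of 30 units took part and unit rates varied with CV 20%, equivalent to ICC = 0.20² × p/(1 − p) = 0.0015. An overall observed/expected test at nominal 5% that ignores unit rejected about 11% for the finite UK target and about 21% for a wider population. A Hosmer-Lemeshow-type test rejected about 7% and 11%.

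**The case against.** The best counter-argument is that this may be a census. The Background counts 30 UK neurosurgery units, section 6 allows for up to 30, and section 7.2.2 rules out sampling. For the average risk in those 30 units, between-unit variation is not sampling error, and the ordinary interval is about right. That stands for full participation and that target. It is not secure, because 30 is a ceiling, and section 8.6 puts the saving on linkage fees at a factor of 20, which suggests about 20 units. A prediction model is also meant for use beyond the data that built it.

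Second, only the protocol is at hand, and variance estimators and bootstrap units are often fixed in an SAP. That also stands as a limit. But section 5 already lists its methods in detail, and nothing there points to handling by unit.

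Third, the only interval named for these two aims is the one per PHASES score, where the effect is small. An overall observed/expected test is not named, although overall calibration is what Aim 1 will be read for. The 759 per unit is also high for Aim 1, which drops patients censored before five years. The pilot averages 6,000/1,415 = 4.2 years.

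Four stronger readings are tempting but unsupported:
- **That the protocol assumes independence, or bootstraps patients.** It is silent on both.
- **That the neurosurgery unit is the unit of sampling.** All identifiable cases are sought, and no sampling of units is described.
- **That verification is expected to fail at some centres.** The text treats this as a contingency.
- **That the sample size wrongly omits a design effect.** An events-per-covariate rule is not a precision calculation.

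**Conclusion.** The point holds in conditional form. The units differ by design in search, period and event confirmation, and no named Aim 1 or Aim 2 analysis reflects this. Whether the intervals are in fact too narrow depends on real variation between units, for which the protocol gives no figure. A reader might infer that they are certainly too narrow; at ICC 0 they are correct.

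The effect matters for pooled UK risk and overall calibration near the planned 22,781 patients: about 86% coverage at ICC 0.001, where units differ by an SD of only 0.6 points around 3.6%. It shrinks toward nominal as participation approaches all UK units with only those as the target. It is slight per PHASES score and at the 1,990-patient minimum. The sentence on internal validity makes no promise about new units, so the point on Aim 2 is that validation across units is missing, which a bootstrap of patients would not supply.

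This should be settled before analysis. It does not invalidate the design.

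**What to change.** **Aim 1.** State that the 95% intervals and calibration statistics, including C and D, use unit as the cluster, by robust variance or by a bootstrap of whole units. With 20 to 30 clusters, use a small-sample correction such as t on K − 1 degrees of freedom. Report the observed/expected ratio by unit with a measure of heterogeneity, and say whether inference is to the participating units, all UK units or beyond.

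**Aim 2.** Keep the Cox model and the absolute risks at 2, 5 and 10 years, with unit-clustered standard errors. Name the bootstrap's resampling unit. Resample whole units, or add leave-one-unit-out (internal-external) validation. Stratifying the baseline hazard by unit is not needed for this: it complicates the absolute risks, and at the 120-event minimum it leaves 120/30 = 4 events per unit.

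**Cost.** A few sentences in section 5 and a little code. The recruiting unit should be known for every record. Intervals for overall UK risk become somewhat wider, with little precision lost if units prove alike. Wider intervals do not remove bias from uneven searching or verification, but the by-unit display would help to reveal it.

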- Population: European/North American, Finnish, Japanese (where race cannot be confirmed it will be assumed to be non-Finnish and non-Japanese on the basis that there is a low incidence of these populations in the UK and their presence would usually be considered noteworthy in a clinical note.

The additional desirable covariates at time of diagnosis will include:

- aspirin use any dose used >3* per week
- statin use any statin use >3* per week
- smoking history non-smoker, ex-smoker, current smoker
- Aneurysm multiplicity record number of intra-dural aneurysms the patient has (treated or untreated)
- Family history number of 1 first degree and second degree relatives with UIA/SAH
- History of Autosomal Dominant Polycystic Kidney Disease yes, no
- Aneurysm location subclassification ICA paraclinoid (ophthalmic and superior hypophyseal) ICA (PCom), ICA other (anterior choroidal and bifurcation), ACA ACOM, ACA pericallosal, MCA, Posterior (basilar termination), Posterior (SCA), Posterior (AICA) Posterior (PICA)
- Bleb or irregularity of aneurysm recorded as present or absent from radiology report only. If not mentioned in report assumed to be absent. If no radiology report available, then recorded as NA.
- New/known diagnosis: patients in whom the aneurysm was known prior to the search period will be recorded as known diagnosis and otherwise as new diagnosis.

Data collection – aneurysm rupture/censoring events – local neurosciences units

At the time of baseline data collection locally available follow up will be recorded which will include:

• Date of last follow-up

- Date of death (if applicable)
- Cause of death (if applicable)
- Date of SAH (if applicable)
- Location of aneurysm causing SAH (if applicable)
- Date of aneurysm treatment (if applicable)
- Reason for aneurysm treatment (if applicable)

This data will be used for quality control of subsequent HES searches.

Data collection - aneurysm rupture/censoring events - central HES ONS data

Upon collection of all baseline data, a search of the Hospital Episode Statistics (HES) and Office for National Statistics (ONS) databases using the patient's NHS numbers be conducted. The use of a HES and ONS search is designed to maximise the identification of rupture events which are not treated in neurosurgical unit as subarachnoid haemorrhage. It will thus identify events managed in a district general hospital or those who die pre-hospital.

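### Unresolved sudden deaths are censored as non-ruptures, and the one analysis that counts them as events covers only Aim 2 and omits I46.1

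*Protocol*

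**What the plan says.** All of this is in Protocol section 5.

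- **Purpose of the linkage** (Data collection, aneurysm rupture/censoring events, central HES ONS data): "It will thus identify events managed in a district general hospital or those who die pre-hospital". One of the three event definitions is "Death diagnosed as subarachnoid haemorrhage in parts 1a-c of the death certificate".
- **Review of sudden deaths** (Data collection, quality assurance, central HES ONS data): the list contains "5. I46.1 sudden cardiac death", then R96 and R98. Patients with these codes "will have their casenotes reviewed to assess if their death was likely due rupture of their aneurysm".
- **Default when verification fails** (same subsection): "any patients with codes in the specified possible miscoded SAH events will be assumed to be non-aneurysmal unless they have a procedure code" for occlusive treatment within 30 days. The other exception applies to patients coded as "subarachnoid haemorrhage other or unspecified and they subsequently died within 30 days", provided no trauma codes are present.
- **Censoring** (Data collection, other considerations; Statistical analysis, Aim 1): death ends follow-up.
- **Aim 1**: causes of underestimation are to be estimated and corrected. If verification fails often at some centres, error estimates from centres that verified well may be used; the code list for this includes I46.1, R96 and R98. A further step compares SAH events in local notes with those in HES over a similar period and adjusts the 5-year risks.
- **Aim 2**: the plan expects some unexplained deaths to remain unresolvable, and as a sensitivity analysis "a model predicting aneurysm rupture or unexplained or unattended death (R 96 and 98) will be built".
- **Aim 3**: Kaplan-Meier curves, proportional hazards models and a cumulative hazard plot, with no statement on unresolved deaths.

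**The concern.** Aims 1 and 3 produce the absolute risks that clinicians would use: the 5-year percentage for each PHASES score, and the long-term rate. These are the results that the default rule lowers. The plan recognises the problem and has devised a suitable analysis, but attaches it only to the Aim 2 prediction model and gives it a shorter code list than its own review step.

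The error runs one way. Because SAH events are verified in notes, the Aim 1 text expects no significant overestimation, so nothing offsets ruptures lost through the default. Section 7.3.2 defends the absence of consent on the ground that losing ruptured patients would bias the risk downward. Unresolved sudden deaths can bring back part of that bias.

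**Working it through.** **Step 1. Follow a death that carries only I46.1, R96 or R98.**

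1. If SAH is in parts 1a-c of the certificate, it is an event.
2. If casenote review judges rupture likely, it is an event.
3. Otherwise the default applies. The first exception needs an occlusive procedure within 30 days after the event, which a patient who has died suddenly will not have. The second needs an I60.8-I60.9 code, which this death does not carry. The death is classed as non-aneurysmal and the patient is censored.

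The loss is therefore confined to deaths that fail both 1 and 2.

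**Step 2. Set the aims side by side.**

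| Aim | Provision for unresolved sudden deaths | Codes |
|---|---|---|
| 1 | Optional correction borrowed from other centres; local-notes versus HES adjustment | I46.1, R96, R98 (optional correction) |
| 2 | Composite of rupture or unexplained/unattended death | R96, R98 |
| 3 | None stated | none |

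**Step 3. Reproduce the plan's planning rate** (section 7.2.1: 51 ruptures, 1,692 patients, 4.1 years).

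- r = 51 / (1,692 × 4.1) = 0.00735 per year.
- Aim 1: 60 × 1,692 / 51 = 1,990.6 patients, and × 4.1 = 8,161 years. The plan states 1,990 and 8,161, so the rate is the plan's own.
- 5-year risk at constant hazard: 1 − exp(−5r) = 3.61%. 30-year risk: 1 − exp(−30r) = 19.8%.
- Ruptures expected in the 113,905 years behind the maximum sample: 113,905 × 0.00735 = 837.

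**Step 4. Illustrate the bias.** The documents give no count of unresolved sudden deaths. Let f be the assumed share of ruptures that end as such deaths and are censored. Reported risk over t years is 1 − exp(−r(1 − f)t).

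| Assumed f | Reported 5-year risk | Reported 30-year risk | Ruptures uncounted of 837 |
|---|---|---|---|
| 0 | 3.61% | 19.8% | 0 |
| 5% | 3.43% | 18.9% | 42 |
| 10% | 3.25% | 18.0% | 84 |
| 15% | 3.08% | 17.1% | 126 |

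**Step 5. Check the Aim 1 mechanism.** Aim 1 calculates risk for patients not censored before 5 years, so an earlier unresolved death appears to leave both numerator and denominator. Per 1,000 patients with 36.09 true ruptures:

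- f = 5%: 34.29 / 998.20 = 3.43%.
- f = 10%: 32.48 / 996.39 = 3.26%.
- f = 15%: 30.68 / 994.59 = 3.08%.

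Dropping these patients has nearly the same effect as censoring them.

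**Step 6. What the bound would look like.** Take 3.61% as the verified risk and suppose u unresolved sudden deaths per 1,000 person-years, all counted as ruptures. The upper bound is 1 − exp(−5(r + u/1000)). For assumed u of 0.1, 0.25, 0.5 and 1.0 it is 3.66%, 3.73%, 3.85% and 4.09%. If unresolved deaths are rare, the bound will show that the default hardly matters.

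**The case against.** Several points on the other side stand.

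- **Not all pre-hospital ruptures are lost.** A reader might infer that they are. Deaths certified as SAH count, and the review asks only whether rupture was likely, which falls short of proof.
- **I46.1 is not invisible throughout.** It is on the review list and on the Aim 1 correction list.
- **Aim 1 is not without remedy.** It makes a general commitment to correct underestimation and has two adjustments. They are weak for these deaths, however. The first is permissive, its trigger is undefined, and it needs other centres that could verify such deaths. The second compares local notes with HES during local follow-up, so a rupture recorded in neither source is not recovered.
- **Most of these deaths may be resolvable.** The documents do not say what the casenotes will contain. The plan expects only some deaths to stay unexplained, so a claim that most will be unresolved is not supported.
- **Omitting I46.1 from the composite can be defended.** The code assigns a cardiac cause, while R96 and R98 are truly unexplained. That supports showing results with and without it. It does not explain a silent omission of a code the plan treats elsewhere as a possible missed rupture.
- **Aim 2 already gives a partial bound.** Its absolute risks can be estimated at 2, 5 and 10 years, so the composite bounds overall risk for R96 and R98. It does not do so by PHASES score or for the Aim 3 curves.
- **Repeating a sensitivity analysis for other aims is often left to an analysis plan.** True, but here the protocol itself fixes the aim and the codes, and fixes them too narrowly.

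**Conclusion.** The point holds in limited form. Sudden deaths coded I46.1, R96 or R98 that are neither certified as SAH nor resolved on review are treated as non-aneurysmal and censored, which biases absolute rupture risk downward. The only analysis counting them as events sits under Aim 2 and omits I46.1. Aim 1 has an optional correction only, and Aim 3 has nothing.

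The size is unknown. The figures of 3.43% to 3.08% against 3.61% rest on an assumed 5% to 15% of ruptures affected, a constant hazard and the plan's own planning rate. The relative shortfall roughly equals the assumed share, so the calculation shows direction and scale and is not evidence that the bias is that large. The share is an average over the cohort and should not be read as applying equally to each PHASES score.

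A reader might infer that the headline risks ignore pre-hospital ruptures, or carry these patients forward as event-free. The documents support neither reading: certified and review-confirmed deaths count, and the remainder are censored at death. This is a cheap improvement that would bound a foreseeable bias; it does not invalidate the design.

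**What to change.** In Protocol section 5, Statistical analysis, replace the Aim 2 composite with one sensitivity endpoint for all three aims: verified rupture, or any unresolved death coded I46.1, R96 or R98.

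- Report it beside the verified-rupture endpoint for the Aim 1 5-year risk per PHASES score, the Aim 2 model and the Aim 3 cumulative-risk curves.
- For Aim 1, state that patients whose unresolved sudden death falls before 5 years stay in the analysis as events under this endpoint. Otherwise the 5-year follow-up requirement would remove them.
- Show results with and without I46.1, because that code will include true cardiac deaths.
- Label the result an upper bound with respect to unresolved sudden deaths. Ruptures certified under other causes remain outside it. Adding fatal unresolved I61 events is optional and would bring in more non-aneurysmal deaths.

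The cost is one repeated analysis for Aims 1 and 3. The codes are already part of the planned search, so no new data are needed. The drawback is that the bound will overstate risk to the extent that it counts deaths from other causes, so it should not be presented as an estimate.
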